6. GENERAL ANALYSIS DEFINITIONS

6.1 TREATMENTS

For basic study information on treatments to be administered, assignment of treatment groups, and selection of doses, cf. Section 4 of the CTP.

Subjects were planned to be treated with

SRD part:

- either a single oral dose of 0.25, 0.75, 2, 5, 10, 20 or 30 mg of BI 1569912 (test treatments)
or
- a single oral dose of placebo (reference treatment)

All placebo subjects will be analysed in one pooled placebo group (i.e. no distinction between dose groups will be made for placebo subjects).

BA/FE part:

- single oral dose of 5 mg BI 1569912 administered as tablet in fed state (test treatment T1) and in fasted state (test treatment T2) and administered as oral solution in fasted state (reference treatment R) with a wash-out period of at least 5 days between treatments

Subjects were randomly assigned to the six treatment sequences.

For statistical analysis of AEs, the following analysis phases are defined for each subject. Analysis phases for active treatments are defined separately for the SRD and BA/FE part.

Table 6.1: 1 Analysis phases for statistical analysis of AEs, and actual treatment for analysis of laboratory data and vital signs for SRD part

Study analysis phase	Label	Start	End
Screening ¹	Screening	Date of informed consent	Date/time of administration of study drug
On treatment	Placebo, 0.25 mg BI, 0.75 mg BI, 2 mg BI, 5 mg BI, 10 mg BI, 20 mg BI, or 30 mg BI, respectively	Date/time of administration of study drug	Date/time of administration of study drug + residual effect period (36 h) or 12:00 a.m. on day after last contact date (whichever occurs first)
Follow-up	F/U Placebo, F/U 0.25 mg BI, F/U 0.75 mg BI, F/U 2 mg BI, F/U 5 mg BI, F/U 10 mg BI, F/U 20 mg BI, or F/U 30 mg BI, respectively	Date/time of administration of study drug + 36 h	12:00 a.m. on day after last contact date

¹ See [Section 6.7](#) for definition of baseline, which will be used in the statistical analyses of safety laboratory data, ECG and vital signs.

Table 6.1: 2 Analysis phases for statistical analysis of AEs, and actual treatment for analysis of laboratory data and vital signs for BA/FE part

Study analysis phase	Label	Start	End
Screening ¹	Screening	Date of informed consent	Date/time of first administration of BI drug
On treatment	BI tab fed, BI tab fasted, BI sol fasted	Date/time of administration of study drug of respective treatment period	Date/time of administration of study drug + REP (36 h) or date/time of administration of study drug in next period or 12:00 a.m. on day after last contact date (whichever occurs first)
Follow-up	F/U BI tab fed, F/U BI tab fasted, F/U BI sol fasted	Date/time of respective treatment administration of BI drug + REP (36 h)	Date/time of administration of study drug of next treatment period or 12:00 a.m. on day after last contact date

¹ See [Section 6.7](#) for definition of baseline, which will be used in the statistical analyses of safety laboratory data, ECG and vital signs.

AE summary tables will present results for the on-treatment phase only. All AEs will be listed.

In AE tables in CTR Section 15.3 (but not in Appendix 16.1.13.1.8.1 and Appendix 16.1.13.1.8.2 AE tables), the following total will be provided in addition:

SRD part:

- **"Total BI SRD"**, defined as the total over all on-treatment phases of the SRD part involving BI
- **"Total on-trt SRD"**, defined as the total over all on-treatment phases of the SRD part, including placebo

BA/FE part:

- **"Total BI BA/FE"**, defined as the total over all on-treatment phases of the BA/FE part involving BI

Safety laboratory data, ECG, qEEG, safety EEG, ERP, CADSS, [REDACTED] and vital signs will be analysed based on treatment groups (SRD part: Placebo, 0.25 mg BI, 0.75 mg BI, 2 mg BI, 5 mg BI, 10 mg BI, 20 mg BI, 30 mg BI) or on treatments in the respective treatment period (BA/FE part: BI tab fed, BI tab fasted or BI sol fasted) with clear differentiation between baseline (cf. [Section 6.7](#)) and post-baseline measurements. Follow-up laboratory measurements will be listed, but will not be used in descriptive summaries.

More details on the technical implementation of these analyses are provided in the ADS Plan of this TSAP.

6.2 IMPORTANT PROTOCOL DEVIATIONS

Consistency check listings (for identification of deviations from time windows) and a list of protocol deviations (e.g. deviations in drug administration, in blood sampling times, etc.) will be provided to be discussed at the Report Planning Meeting. At this meeting, it will be decided whether a discrepant data value can be used in analyses or whether it must be corrected in the clinical database. Each protocol deviation must be assessed to determine whether it is an important PD (IPD). For definition of IPDs, and for the process of identification of these, refer to the BI reference document "Identify and Manage Important Protocol Deviations (IPD)" ([2](#)).

If any IPDs are identified, they are to be summarised into categories and will be captured in the decision log. Categories which are considered to be IPDs in this trial are defined in the DV domain template. If the data show other IPDs, the definition in the DV domain template will be supplemented accordingly by the time of the Report Planning Meeting.

IPDs will be summarized and listed. Which kind of IPDs could potentially lead to exclusion from which analysis set is specified in the DV domain template. The decision on exclusion of subjects from analysis sets will be made at the latest at the Report Planning Meeting, after discussion of exceptional cases and implications for analyses. If the data show other IPDs, this table will be supplemented accordingly by the time of the Report Planning Meeting.

Non-important COVID-19 related PDs will only be listed.

6.3 SUBJECT SETS ANALYSED

[figure not shown]
The treated set (TS) and pharmacokinetic parameter analysis set (PKS) will be used as defined in Section 7.3 of the CTP. In addition, the following subject set will be used.

[REDACTED]

Table 6.3: 1 Subject sets analyzed

Class of endpoint	Subject set		
	TS	PKS	
Primary endpoint (SRD part)	X		
Primary endpoint (BA/FE part)		X	
Secondary PK endpoints		X	
Safety parameters	X		
Demographic/baseline characteristics	X		
Treatment exposure	X		

6.5 POOLING OF CENTRES

This section is not applicable, because the study was performed in only one centre.

6.6 HANDLING OF MISSING DATA AND OUTLIERS

CTP: “If a subject is removed or withdraws from the trial prior to the first administration of trial medication, the data of this subject will not be entered in the case report form (CRF) and will not be reported in the clinical trial report (CTR). If a subject is removed or withdraws from the trial after the first administration of trial medication, this will be documented and the reason for discontinuation must be recorded in the CRF. In addition, the data will be included in the CRF and will be reported in the CTR.”

CTP: “It is not planned to impute missing values for safety parameters.”

One exception where imputation might be necessary for safety evaluation is AE dates. Missing or incomplete AE dates are imputed according to BI standards (3).

No imputation will be done for ECG endpoints. If replicate ECG recordings are missing, the arithmetic means per time point will be computed with the reduced (1 or 2) number of recordings. If single cardiac cycles (also denoted as beats or waveforms) are missing, the arithmetic mean per single ECG will be computed with the reduced (1, 2 or 3) number of cardiac cycles.

For the classification of the on-treatment QTc/QT intervals into ‘no new onset’ / ‘new onset’ categories, the handling of missing value is described in [Section 10.3](#).

Missing data and outliers of PK data are handled according to BI standards ([4](#)) and ([5](#)).

CTP: Pharmacokinetic parameters that cannot be reasonably calculated based on the available drug concentration-time data will not be imputed.

6.7 BASELINE, TIME WINDOWS AND CALCULATED VISITS

In all analyses (except for analyses of PD endpoints and analyses of ECG variables), the last available off-treatment value determined prior to the dosing of the respective study drug will be defined as baseline. This means that a separate baseline is defined for each study treatment of the BA/FE part. Off-treatment in this context means that a value measured within an on-treatment phase, as defined in [Table 6.1: 2](#), will not be used as baseline for any study treatment.

Table 6.7: 1 Baseline for [REDACTED] and ERP endpoints

Post-baseline value		Corresponding baseline value	
Planned time	Clock time	Planned time	Clock time
4:00	12:00	-20:00	12:00
24:00	08:00	-24:00	8:00
48:00	08:00	-24:00	8:00
72:00	08:00	-24:00	8:00

Table 6.7: 2 Baseline for qEEG endpoints

Post-baseline value		Corresponding baseline value	
Planned time	Clock time	Planned time	Clock time
0:45	08:45	-23:00	09:00
1:15	09:15	-23:00	09:00
3:00	11:00	-21:00	11:00
8:00	16:00	-16:00	16:00
24:00	08:00	-23:00	09:00
48:00	08:00	-23:00	09:00
72:00	08:00	-23:00	09:00

Table 6.7: 3 Baseline for additional analysis of qEEG endpoints, using first value after drug administration as baseline

Post-baseline value		Corresponding baseline value	
Planned time	Clock time	Planned time	Clock time
1:15	09:15	0:45	08:45
3:00	11:00	0:45	08:45

A centralised evaluation of 12-lead ECG recordings is performed at the time points specified in [Table 6.7: 4](#) for the SRD part and in [Table 6.7: 5](#) for the BA/FE part.

Table 6.7: 4 Time schedule of 12-lead ECG recordings with centralised evaluation (SRD part)

Visit	Day	Planned time [hh:mm] - relative to first drug administration	Study phase
2	-1	-25:00	Baseline
	1	00:30	On-treatment
		01:10	
		01:30	
		02:00	
		03:00	
		04:00	
		06:00	
		08:00	
		12:00	
	2	24:00	
		34:00	
	3	48:00	Follow-up
	4	72:00	

Table 6.7: 5 Time schedule of 12-lead ECG recordings with centralised evaluation (BA/FE part)

Visit	Day	Planned time [hh:mm] - relative to first drug administration	Study phase
2/3/4	-1	-25:00	Baseline
	1	00:30	On-treatment
		01:05	
		02:00	
		04:00	
		08:00	
	2	24:00	Follow-up
	3	48:00	
	4	72:00	

Three triplicate ECGs will be recorded as the baseline before the first drug administration within each treatment period. Within each triplicate, the mean of ECG variables will be calculated. The mean over the three triplicates will be used as baseline for ECG variables.

For subjects from 30 mg dose group, only the first ECG of each of the 3 baseline triplicates of that period will be transferred to the database. The mean over the three triplicates will be used as baseline for ECG variables in this dose group.

Additional (unscheduled) ECGs may be recorded for safety reasons. These ECGs are assigned to the prior scheduled time point in the sponsor's database. Unscheduled ECGs (for safety reasons) will be transferred to the central ECG lab but will not be included into the statistical analysis of interval lengths.

Time windows are defined in Section 6.1 of the CTP. Adherence to time windows will be checked at the Report Planning Meeting.

7. PLANNED ANALYSIS

The format of the listings and tables will follow the BI guideline "Reporting of clinical trials and project summaries" ([6](#)).

The individual values of all subjects will be listed. Listings will be sorted by treatment or sequence group, subject number and visit (if visit is applicable in the respective listing). AE listings will be sorted by assigned treatment (see [Section 7.8.1](#) below for details). The listings will be contained in Appendix 16.2 (SDL) of the CTR.

The following standard descriptive statistical parameters will be displayed in summary tables of continuous variables:

N	number of non-missing observations
Mean	arithmetic mean
SD	standard deviation
Min	minimum
Median	median
Max	maximum

For plasma concentrations as well as for all PK parameters the following descriptive statistics will additionally be calculated:

CV	arithmetic coefficient of variation
gMean	geometric mean
gCV	geometric coefficient of variation

For PK parameters the following descriptive statistics will additionally be calculated:

P10	10 th percentile
Q1	1 st quartile
Q3	3 rd quartile
P90	90 th percentile

The data format for descriptive statistics of plasma concentrations will be identical with the data format of the respective concentrations. The descriptive statistics of PK parameters will be calculated using the individual values with the number of decimal places as provided by the evaluation program. Then the individual values as well as the descriptive statistics will be reported with three significant digits in the CTR.

Tabulations of frequencies for categorical data will include all possible CRF categories and will display the number of observations in a category as well as the percentage (%) relative to the respective treatment group. Percentages will be rounded to one decimal place. The category missing will be displayed if and only if there actually are missing values. Percentages will be based on all subjects in the respective subject set whether they have non-missing values or not.

7.2 CONCOMITANT DISEASES AND MEDICATION

Concomitant diseases will be coded according to the most recent version of MedDRA. Concomitant medication will be coded according to the most recent version of the World Health Organisation – Drug Dictionary. Concomitant non-drug therapies will be coded according to the most recent version of MedDRA.

Only descriptive statistics are planned for this section of the CTR.

CTP: *Previous and concomitant therapies will be presented per treatment group without consideration of time intervals and treatment periods.*

A medication will be considered concomitant to a dose group, if it

- is ongoing at the time of study drug administration, or
- starts within the analysis phase of the respective treatment (see [Section 6.1](#) for a definition of treatments and analysis phases).

The relevance of the concomitant therapies to the evaluation of PK will be decided no later than at the RPM.

7.4 PRIMARY ENDPOINTS

7.4.1 Primary analysis of the primary endpoints

SRD part:

Refer to [Section 7.8.1](#) for a description of the analysis of AEs, and in particular the analysis of the percentage of subjects with treatment-emergent drug related AEs, which is the primary endpoint of this trial in the SRD part.

BA/FE part:

CTP: *The statistical model used for the analysis of the primary endpoints will be an analysis of variance (ANOVA) model on the logarithmic scale. That is, pharmacokinetic endpoints will be log-transformed (natural logarithm) prior to fitting the ANOVA model. This model will include effects accounting for the following sources of variation: sequence, subjects within*

sequences, period and treatment. The effect 'subjects within sequences' will be considered as random, whereas the other effects will be considered as fixed. The model is described by the following equation:

$$y_{ijkm} = \mu + \zeta_i + s_{im} + \pi_j + \tau_k + e_{ijkm}, \text{ where}$$

$$y_{ijkm} = \text{logarithm of response measured on subject } m \text{ in sequence } i \text{ receiving treatment } k \text{ in period } j,$$

$$\mu = \text{the overall mean,}$$

$$\zeta_i = \text{the } i\text{th sequence effect, } i = 1, \dots, 6$$

$$s_{im} = \text{the effect associated with the } m\text{th subject in the } i\text{th sequence, } m = 1, 2, \dots, n_i$$

$$\pi_j = \text{the } j\text{th period effect, } j = 1, 2, 3$$

$$\tau_k = \text{the } k\text{th treatment effect, } k = 1, 2, 3$$

$$e_{ijkm} = \text{the random error associated with the } m\text{th subject in sequence } i \text{ who received treatment } k \text{ in period } j.$$

where $s_{im} \sim N(0, \sigma_B^2)$ i.i.d., $e_{ijkm} \sim N(0, \sigma_W^2)$ i.i.d. and s_{im} , e_{ijkm} are independent random variables.

Point estimates for the ratios of the geometric means (T1/ T2 and T2/ R) for the primary endpoints (see Section 2.1) and their two-sided 90% confidence intervals (CIs) will be provided.

For each endpoint, the difference between the expected means for $\log(T)$ - $\log(R)$ will be estimated by the difference in the corresponding adjusted means (Least Squares Means). Additionally their two-sided 90% confidence intervals will be calculated based on the residual error from the ANOVA and quantiles from the t -distribution. These quantities will then be back-transformed to the original scale to provide the point estimate and 90% CIs for each endpoint.

The analysis of primary endpoints of the BA/FE part will be based on the PKS.

Exclusion of PK parameters

The ADS ADPP contains column variables APEXC and APEXCO indicating inclusion/exclusion (APEXC) of a PK parameter and an analysis flag comment (APEXCO). All analyses based on the PKS are based on PK parameter values which are not flagged for exclusion, i.e. with APEXC equal to "Included".

CTP: Plasma/urine concentration data and parameters of a subject which is flagged for exclusion will be reported with its individual values but will not be included in the statistical analyses.

Exclusion of plasma concentrations

The ADS ADPC (PK concentrations per time-point or per time-interval) contains column variables ACEXC or ACEXCO indicating inclusion/exclusion (ACEXC) of a concentration and an analysis flag comment (ACEXCO). Exclusion of a concentration depends on the analysis flag comment ACEXCO. For example, if ACEXCO is set to "ALL CALC", the value will be excluded for all types of analyses based on concentrations. If ACEXCO is set to "DESC STATS" the value will be excluded from descriptive evaluations per planned time point/time interval. If ACEXCO contains the addition "TIME VIOLATION" or "TIME DEVIATION", the value can be used for further analyses based on actual times. If ACEXCO is set to "HALF LIFE", the value will be excluded from half-life calculation only; the value is included for all other analyses. Excluded concentration itself will be listed in the CTR associated with an appropriate flag.

Further details are given in "Noncompartmental PK/PD Analyses of Clinical Studies"[\(4\)](#) and "Description of Analytical Transfer Files and PK/PD Data Files" [\(5\)](#).

[REDACTED]

[REDACTED]

[REDACTED]

[REDACTED]

[REDACTED]

[REDACTED]

7.5 SECONDARY ENDPOINTS

7.5.1 Key secondary endpoints

This section is not applicable as no key secondary endpoint has been specified in the protocol.

7.5.2 Secondary endpoints

The analysis of secondary endpoints will be based on the PKS.

[figure not shown]
7.5.2.1 Secondary endpoint analysis

[figure not shown]
SRD part:

The PK endpoints will be assessed descriptively. Analyses will be performed for the parent drug and for metabolites. The analysis of standard PK parameters is performed according to BI standards ([4](#)). Exclusion of PK parameter and exclusion of plasma concentrations are handled as described in [Section 7.4.1](#).

BA/ FE-Part:

CTP: The secondary endpoints (refer to Section 2.1.3) will be [...] assessed statistically using the same methods as described for the primary endpoints.

7.8 SAFETY ANALYSIS

All safety analyses will be performed on the TS.

7.8.1 Adverse Events

AEs will be coded with the most recent version of MedDRA.

The analyses of AEs will be descriptive in nature. All analyses of AEs will be based on the number of subjects with AEs and not on the number of AEs.

For further details on summarization of AE data, please refer to "Analysis and Presentation of Adverse Event Data from Clinical Trials" (7) and "Handling of missing and incomplete AE dates" (3).

The analysis of AEs will be based on the concept of treatment emergent AEs. That means that all AEs will be assigned to screening, on-treatment or follow-up phases as defined in [Section 6.1](#). AEs will be analysed based on actual treatments, as defined in [Table 6.1: 1](#) and [Table 6.1: 2](#).

An overall summary of AEs will be presented. This overall summary will comprise summary statistics for the class of AESIs.

CTP: *The following are considered as AESIs:*

- *Hepatic injury*
A hepatic injury is defined by the following alterations of hepatic laboratory parameters:
 - *An elevation of AST (aspartate transaminase) and/or ALT (alanine transaminase) ≥ 3 fold ULN combined with an elevation of total bilirubin ≥ 2 fold ULN measured in the same blood sample, or*
 - *Aminotransferase (ALT, and/or AST) elevations ≥ 10 fold ULN*

The investigator had to classify on the eCRF whether an observed AE was an AESI or not.

According to ICH E3 (8), in addition to Deaths and Serious Adverse Events, 'other significant' AEs need to be listed in the clinical trial report. These will be any non-serious adverse event that led to an action taken with study drug (e.g. discontinuation or dose reduced or interrupted).

The frequency of subjects with AEs will be summarised by treatment, primary SOC and preferred term. AEs which were considered by the investigator to be drug related will be summarised separately. Separate tables will also be provided for subjects with SAEs and subjects with AESIs. AEs will also be summarized by maximum intensity.

The SOC and preferred terms within SOC will be sorted by descending frequency over all treatment groups.

For disclosure of AE data on ClinicalTrials.gov, the frequency of subjects with non-serious AEs occurring with an incidence of greater than 5 % (in preferred terms) will be summarised by treatment, primary SOC and preferred term. The frequency of subjects with SAEs will also be summarised.

For disclosure of AE data in the EudraCT register, the frequency of AEs, the frequency of non-serious AEs with an incidence of greater than 5 % (in preferred terms) and the frequency of SAEs will be summarized.

For support of lay summaries, the frequency of subjects with drug-related SAEs will be summarized by treatment, primary SOC and preferred term.

7.8.2 Laboratory data

The analyses of laboratory data will be descriptive in nature and will be based on BI standards "Handling, Display and Analysis of Laboratory Data" (9).

Analyses will be based on normalised values, which means transforming to a standard unit and a standard reference range. The original values will be analysed if the transformation into standard unit is not possible for a parameter.

Descriptive statistics of baseline and on-treatment laboratory values over time and for the difference from baseline (see [Section 6.7](#)) will be provided. Frequency tables of changes between baseline and last value on treatment with respect to the reference range will be presented.

Unscheduled measurements of laboratory data will be assumed to be repeat measurements of the most recent scheduled measurement (e.g. for follow-up or confirmation of a particular value). Therefore, unscheduled measurements will be assigned to the planned time point of the previous scheduled measurement. Descriptive statistics will be calculated by planned time point based on the worst value of the subject at that planned time point (or assigned to that planned time point).

Laboratory data will be compared to their reference ranges. Values outside the reference range as well as possibly clinically significant values will be highlighted in the listings.

Clinically significant abnormal laboratory values are only those identified either in the Investigator's comments or at the Report Planning Meeting at the latest. It is the Investigator's responsibility to decide whether a lab value is clinically significant abnormal or not. Standard or project-specific rules for flagging clinically significant values in an automated manner will

not be applied in this study. Clinically relevant findings in laboratory data will be reported as baseline conditions (prior to first administration of study treatment) or as AEs (after first administration of study treatment) if judged clinically relevant by the investigator, and will be analyzed as such.

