|       |         | 34:00  | 18:00  |  |                   | x                                     | —                                    |           |                                   |        |                 |     |   | X  |                           | x                           |  |
|       | 3       | 48:00  | 08:00  |  |                   | x                                     | ▼                                    | x         |                                   |        | x  | x   | ■ | X  |                           | x                           |  |
|       | 4       | 72:00  | 8:00   | Breakfast (voluntary) 
Discharge from trial site | B    | x                                     |                                      | x         | x                                 | x      | x  | x   | ■ | X  |                           | x                           | ▼  |
| 5     | 4 to 14 |  |  | End of trial (EoT) examination                             | A                 |                                       |                                      |           | x                                 |        |                 |     |   | x               |                           | x                           | x   |

- Subject must be informed and written informed consent obtained prior to starting any screening procedures. Screening procedures include physical examination, check of demographics (including determination of body height and weight, smoking status and alcohol history), relevant medical history, concomitant therapy and review of inclusion/exclusion criteria.
- The time is approximate; procedures are to be performed and completed within the 3 h prior to drug administration. Allocation to treatment may be performed at any time following enrolment but must be completed prior to (first) drug administration.
- If several actions are indicated at the same time, the intake of meals will be the last.
- EoT examination includes physical examination, body weight, vital signs, ECG, safety laboratory, recording of AEs, and concomitant therapies.
- Only urine drug screening and alcohol breath test will be done at this time.
- AEs and concomitant therapies will be recorded throughout the trial, but will be specifically asked for at the times indicated in the [Flow Chart](#) above.

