### 1.2.5 Prediction of human pharmacokinetics

A human clearance of 2.89 mL/min/kg was predicted based on in vitro-in vivo correlation. A human volume of distribution at steady state of 0.678 L/kg was predicted based on mean of animals. These resulted in a predicted human disposition mean residence time and effective half-life of 3.91 h and 2.7 h, respectively, and single therapeutic dose of 2.0 mg (free base) to achieve a Cmax of 52 nM in human.

Human therapeutic dose of 2.0 mg is predicted based on a minimum effective total plasma concentration of 52 nM in the mouse FST. Considering similar potency in human compared with the mouse, and no significant difference in protein binding between both species, this also translates into an anticipated effective total plasma concentration of approximately 52 nM, which was set as target  $C_{\max}$  for the prediction of human pharmacokinetics and dose.

A summary of the predicted human pharmacokinetic parameters and therapeutic dose is presented in Table [1.2.5: 1](#).

Table 1.2.5: 1 Summary of the predicted pharmacokinetic parameters and therapeutic dose of BI 1569912 in human

| Parameters                          | Prediction |
|-------------------------------------|------------|
| CL [mL/min/kg]                      | 2.89       |
| $V_{ss}$ [L/kg]                     | 0.678      |
| MRT disp [h]                        | 3.91       |
| F [%]                               | 58.2       |
| MAT [h]                             | 2.09       |
| $k_a$ [h  ]            | 2.47       |
| MRT tot [h]                         | 5.99       |
| $t_{\max}$ [h]                      | 1.39       |
| $t_{1/2,eff}$ [h]                   | 2.7        |
| Exposure target ( $C_{\max}$ ) [nM] | 52         |
| AUC 0-inf [nM*h]         | 330        |
| $C_{\max}$ [nM]                     | 52         |
| Therapeutic dose [mg]               | 2.0        |

Source data: [\[n00272965\]](#)

For further information, see current IB [\[c29289852\]](#).

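### The laboratory shift table uses only the last on-treatment value, normally the 24-h sample, so the SAP text plans no count of subjects newly out of range at 4 h

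*SAP*

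**What the plan says.** SAP 7.8.2 (Laboratory data) plans three kinds of display.

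- Descriptive statistics of values and changes from baseline over time. Where a subject has repeats, these are "based on the worst value of the subject at that planned time point".
- Shift tables: "Frequency tables of changes between baseline and last value on treatment with respect to the reference range will be presented".
- Listings with out-of-range values highlighted. Findings that the investigator judges clinically relevant are handled as AEs.

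The meaning of on treatment comes from SAP 6.1. In the SRD part the phase ends at "Date/time of administration of study drug + residual effect period (36 h" after dosing, or at last contact if that is earlier. In the BA/FE part it ends at "Date/time of administration of study drug + REP (36 h" in each period, or at the next dose or last contact if earlier. The title of the SRD table, "Analysis phases for statistical analysis of AEs, and actual treatment for analysis of laboratory data and vital signs for SRD part", says that these phases also govern laboratory data, and the title of the BA/FE table does the same. For later samples SAP 6.1 adds: "Follow-up laboratory measurements will be listed, but will not be used in descriptive summaries".

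Both protocol flow charts schedule safety laboratory panel B at 4 h, 24 h and 72 h after dosing, and panel A at the end-of-trial visit.

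**The concern.** Comparing baseline with the last on-treatment value suits repeated dosing, where the last sample is taken under continuing exposure. After a single dose of a drug with a predicted short half-life, the last sample in the window is the one with the least drug on board. A shift that is present at 4 h and gone by 24 h does not enter the table.

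The SAP's other categorical safety displays do not work this way. The categorical ECG endpoints in SAP 5.3.1 use the maximum over all on-treatment time points, and SAP 7.8.1 summarises AEs by maximum intensity. SAP 7.8.2 also states that no automated rule will flag clinically significant laboratory values. The shift table is thus the only frequency table against the reference range that the SAP text specifies. At stake is whether a reader comparing dose groups of six active subjects with pooled placebo can see how many subjects moved out of range at the early sample.

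**Working it through.** **Step 1: which samples are on treatment.** Scheduled post-dose panels are at 4 h, 24 h and 72 h, then end of trial. The window is 36 h. Since 4 < 36 and 24 < 36, those two are on treatment. Since 72 > 36, the 72-h sample is follow-up, which is listed only. The last scheduled on-treatment value is the 24-h sample, in the SRD part and in each BA/FE period. An unscheduled repeat between 24 h and 36 h is assigned to the 24-h time point. The 4-h value becomes the last value only if no 24-h value or later on-treatment repeat exists.

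**Step 2: what each rule shows.** For a subject with a normal baseline (N = in range, A = out of range):

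| 4 h | 24 h | Planned table (last value) | Table by time point |
|---|---|---|---|
| N | N | no shift | none |
| N | A | shift | shift at 24 h |
| A | N | **no shift** | **shift at 4 h** |
| A | A | shift | shift at 4 h and 24 h |

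Only the third pattern is hidden from the planned table. This step needs no pharmacokinetic assumption.

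**Step 3: exposure at the two samples.** Protocol 1.2.5 predicts tmax of 1.39 h and gives disposition mean residence time and "effective half-life of 3.91 h and 2.7 h, respectively". Protocol 1.2.7 works with about 3 h. Assuming simple exponential decline from dosing, which is rough for an oral dose, the fraction left is 0.5^(t / half-life):

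| Half-life | 4 h | 24 h | 24 h as half-lives | 24-h level as % of 4-h level |
|---|---|---|---|---|
| 2.7 h | 35.8% | 0.21% | 8.9 | 0.6% |
| 3.0 h | 39.7% | 0.39% | 8.0 | 1.0% |

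The last column is 2^(−20 / half-life). The 4-h sample is the scheduled one nearest peak exposure.

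**Step 4: illustration only.** The documents give no laboratory variability or effect size, so all inputs here are assumed: a normally distributed analyte, upper limit at 1.96 total SD, within-subject SD half the total SD, and baseline not above the limit.

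| Assumed rise at 4 h | Assumed rise at 24 h | Newly high at 4 h | Newly high at 24 h (planned table) |
|---|---|---|---|
| none | none | 1.6% | 1.6% |
| 1 SD | none | 15% | 1.6% |
| 2 SD | none | 50% | 1.6% |
| 2 SD | 0.5 SD | 50% | 5.7% |

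With no effect, taking the worse of the two samples raises 1.6% to 2.8%.

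**Step 5: chance shifts over the panel.** Panel B in protocol Table 5.2.3: 1 has about 44 quantitative analytes (17 haematology including differentials, 3 coagulation, 9 enzymes without the conditional CK-MB, 10 substrates, 5 electrolytes). Counting both directions for six active subjects, under the Step 4 assumptions:

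- one time point: 44 × 6 × 2 × 0.016 ≈ 8.4 chance shifts;
- worst of two samples: 44 × 6 × 2 × 0.028 ≈ 14.8.

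A table by time point adds a second set of about 8.4, shown apart from the 24-h set and not merged with it.

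**The case against.** The strongest reply is that little is lost and that a worst-value table would be worse.

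- **The 4-h signal is visible elsewhere.** This stands. Statistics by time point include minimum and maximum (SAP 7), out-of-range values are highlighted in listings, relevant findings are tabulated as AEs, and hepatic alerts have their own AESI table. A reader might infer that the early signal is removed from the report, but the documents do not support that. Only a count is missing.
- **The two laboratory rules do not conflict.** This stands. A reader might see the worst-value and last-value rules as opposites. The worst-value rule settles repeats within one planned time point, whereas the last-value rule selects the time point.
- **Laboratory change need not track plasma level.** This stands. It is tempting to say that the table shows recovery and not drug effect. Slow changes still out of range at 24 h are captured. The 36-h period was chosen because of a convulsion in a dog at 28 h (protocol 1.2.7), and the enzyme rises in protocol 1.2.3.2 occurred in dogs with convulsions beginning about 24 h after dosing.
- **The 24-h sample is the closer match to baseline.** This largely stands. The scheduled Day -3 panel and the 24-h panel are both at 08:00, and the 4-h panel is at 12:00. Protocol 4.2.2.2 gave SRD subjects a light breakfast about 2 h after dosing until Amendment 7, and T1 subjects eat a high-fat breakfast 30 min before dosing. Merging the two samples would mix these influences into one figure and raise chance shifts (Step 5). This argues against replacing the planned table, but not against a separate 4-h table in which pooled placebo meets the same SRD conditions.
- **The sponsor's laboratory standard may add displays.** It is cited in SAP 7.8.2 but is not available here. The finding is therefore limited to what the SAP text specifies.

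**Conclusion.** The point holds as a minor gap in a descriptive safety display. On the SAP's own definitions, the shift table cannot count a subject who is out of range at 4 h and back in range at 24 h, unless an out-of-range repeat follows the 24-h sample. The SAP text provides no other count by treatment of such subjects. This conclusion rests only on the sampling schedule, the 36-h window and the last-value rule. The view that 4 h is the more exposed sample rests on predicted pharmacokinetics, although SAP 4 also describes the observed profile as steep.

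The size in this trial cannot be estimated, because the documents give no laboratory variability or effect. A reader might take the illustrative percentages as expected losses, but they follow from assumed rises of 1 or 2 SD. Nor is this an error in a primary analysis: the SRD primary endpoint is drug-related AEs, and the BA/FE primary endpoints are pharmacokinetic.

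**What to change.** In SAP 7.8.2, keep the baseline-to-last table and add the same reference-range shift table by planned on-treatment time point (4 h and 24 h), with shifts to low and to high shown separately. Present it for each SRD treatment, including pooled placebo, and for each BA/FE treatment. Add a footnote that 4-h values can reflect meals (light breakfast in SRD groups dosed before Amendment 7, high-fat breakfast in T1) and time of day.

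The cost is a sentence in the SAP and one more descriptive table from data already collected. The downside is more chance shifts across the many analytes, so the added table should be read against placebo in the SRD part and not cell by cell. The BA/FE part has no placebo, so its 4-h counts can only be compared between treatments, with the meal difference in mind.
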